4.2. Adherence and protocol deviations

4.2.1. Definitions of protocol deviations

Any alteration or modification to the IRB-approved research without prospective IRB approval. The term research encompasses all IRB-approved materials and documents including the detailed protocol, IRB

application, consent form, recruitment materials, questionnaires/data collection forms, and any other information relating to the research study.

4.2.2. Adherence and protocol deviations to be summarized

As a pragmatic study, all levels of adherence are allowed. Compliance with the study-recommended medication and dosing will be assessed at each decision support call using the Protocol Adherence Form. Reasons for non-compliance will be documented.

4.2.3. Electronic Data Capture

This study will utilize REDCap-based electronic Case Report Forms (e-CRF's) for data capture and storage. Source documents, including laboratory values, medical records and physician communications will be maintained at each site to verify adherence to protocol, inclusion/exclusion criteria, and data accuracy.

4.3. Analysis populations

We will follow the intention-to-treat (ITT) principle. In other words, patients who receive co-prescribed medications, stop randomized medication, or switch to a different medication will continue to be followed. To confirm that ITT findings represent the "true" data on effectiveness, safety, and tolerability of management strategies, we will conduct a sensitivity analysis that will compare ITT to per-protocol findings.¹

5. Trial Population

5.1. Screening data

Potential participants identified through each site's IRB-approved recruitment plans will be screened for eligibility. Staff and PI's at each site are responsible for verifying that participants at their site meet all eligibility criteria before being randomized to acute treatment. We anticipate differences between sites in which assessments may be obtained in pre-screening (pre-written consent) versus screening (post written consent). Despite these potential differences, the following assessments must be conducted prior to randomization to ensure eligibility (see also Section 5.2.1 and 5.2.2 for Inclusion and Exclusion Criteria):

- PHO-9
- MINI MDE Module
- Screening questions for treatment resistance and medical exclusions
- Short Blessed Test
- ATHF
- CIRS-G

5.2. Eligibility

All participants will meet the following eligibility criteria:

5.2.1. Inclusion Criteria (Steps 1 & 2)

a) Men and women aged 60 and older.

¹ In the course of conducting analyses of effectiveness, the research team noted that many participants had a prior trial of one of the randomized medications. This was allowed per the study protocol. Because of these, a sensitivity analysis was conducted examining remission rates and change in depression scores for only those participants who had not had a prior trial of one of the randomized treatments. This was only done for Step 1, because Step 2 treatments were rarely used in prior trials.

- b) Current Major Depressive Disorder (MDD), single or recurrent, as diagnosed by DSM-5 criteria.
- c) Failure to respond adequately to two or more antidepressant treatment trials of recommended dose and length (approximately 12 weeks; minimum 4 weeks at adequate dose).
- d) PHQ-9² score of 10 or higher.

5.2.2. Exclusion Criteria (Steps 1 & 2)

- a) Inability to provide informed consent.
- b) Dementia, as defined by Short Blessed ≥10 and/or clinical evidence of dementia. Patients screened out due to possible dementia will be referred to a local Memory Clinic or back to their clinician for evaluation to clarify the presence or absence of dementia.
- c) Lifetime diagnosis of bipolar I or II disorder, schizophrenia, schizoaffective disorder, schizophreniform disorder, delusional disorder, or current psychotic symptoms. A recommendation for psychiatric referral will be made in these cases.
- d) High risk for suicide (e.g., active suicide ideation and or current/recent intent or plan) and unable to be managed safely in the clinical trial, such as unwilling to be hospitalized). Urgent psychiatric referrals will be made in these cases.
- e) Contraindication to proposed study medications, as determined by study physician including history of intolerance or non-response to proposed medications.
- f) Non-correctable, clinically significant sensory impairment (e.g., cannot hear well enough to cooperate with interview).
- g) Unstable medical illness, including delirium, uncontrolled diabetes mellitus, hypertension, hyperlipidemia, or cerebrovascular or cardiovascular risk factors that are not under medical management. This will be determined based on information from the patient's personal physician's and study physician clinical judgment. Referral to the patient's personal physician or to a general practitioner will be made in these cases.
- h) Moderate to severe substance or alcohol use disorder, as determined by study physician. Referral to appropriate treatment will be made in these cases.
- i) Seizure disorder.³
- j) Parkinson's Disease³

No exclusion criteria are based on race, ethnicity, or gender.

5.2.3. Exclusions to Enter Step 2⁴

The following conditions are contraindications to Step 2 medications. Participants with them will not be eligible for Step 2 participation (but may be considered for Step 1 provided they meet criteria outlined in study protocol Sections 2.a & 2.b.)

² Initially the investigators used a score of 6 or greater but, per discussion with PCORI methodology team, changed this to 10 or greater during the study.

³ When participants were allowed direct entry to Step 2, exclusion criteria i) and j) were exclusion for Step 1 only.

[figure not shown]
⁴ The investigators allowed eligible individuals to directly enter Step 2 (i.e. if ineligible for Step 1). Thus, participants could enter from Step 1 or directly from initial consent into the study.

- a) QTC prolongation or Wide QRS on EKG
- b) Active Ischemic Heart Disease as evidenced by angina or requiring treatment (e.g., nitrates) for ischemic attacks. Patients with history of prior MI, stent, or bypass may be included who have had no symptoms of ischemia (e.g., no chest pain) for 2 years.
- c) Acute or chronic renal insufficiency (as indicated by creatinine clearance below 30 mL/min; suspected if creatinine above 1.5 mg/dL; per PI and/or clinician discretion)
- d) Narrow-angle glaucoma

5.3. Recruitment

A Consort diagram will be used to visualize the flow of patients. We will report the number of eligible participants and the number of screened participants. The reasons for lack of eligibility will be enumerated. The number randomized will be reported as well as the reasons for non-randomization. The number randomized into each of the three arms (augmentation with aripiprazole, augmentation with bupropion, and switch to bupropion) will be reported. For those who do not remit under step 1 will be randomized in step 2 to one of 2 arms (augmentation with lithium and switch to nortriptyline). See Figure 1.

Figure 1.

^{*}sample size estimated mid-study

5.4. Withdrawal/follow-up

5.4.1. General withdrawal rules

Participants will be asked to continue in the study for follow-up regardless of their and their physician's adherence to the medication recommendations from the study team. Participants who discontinue study medications for tolerability reasons will be asked to complete the appropriate Acute Phase End Assessments for their phase of the study. Participants who end Step 1 treatment early due to tolerability issues will be invited to proceed to Step 2 after completing Acute Phase End Assessments.

Participants who choose to withdraw from the study early will be asked to complete the appropriate final visit for their phase of the study (Step 1 acute endpoint, Step 2 acute endpoint, or Continuation Month 12).

Statistical Analysis Plan OPTIMUM

Withdrawal from the study for any reason, including study completion, will be documented in the Electronic Case Report Form.

Participants' reasons for withdrawal will be summarily reviewed by each site's IRB at Continuing Review and at DSMB meetings.

5.5. Baseline participant characteristics

5.5.1. List of baseline characteristics

Informed consent forms will be signed by participants at baseline. Local research team assessments elements collected during baseline:

- MINI MDD & Bipolar Modules
- o PHQ-9 (If more than 7 days has elapsed since the PHQ-9 was done at pre-screen.)
- Suicide History, Risk & Protective Factors
- o Baseline Side Effects
- Expectations for Adherence
- o Falls & Fall-related Injuries (history)
- Height and Weight (self-reported)
- o If indicated by pre-screen: DAST-10
- o If indicated by pre-screen: AUDIT
- o NIH Toolbox Psychological Well Being (general life satisfaction and positive affect scales)
- o PROMIS Physical Function
- o PROMIS Social Participation
- o PROMIS Anxiety
- NIH Cognition and Motor Batteries (in-person assessments may be foregone for participants living in remote locations)
- o ATHF
- o CIRS-G
- Medical Conditions and Medication List (study doctor to review before randomization)
- o MADRS

The key variables being used in the study include:

- o Age
- o Gender
- o Race
- o Ethnicity
- o CIRS-G (cumulative medical comorbidity)
- o MADRS
- o PHQ-9
- o ATHF

5.5.2. Descriptive summarization of baseline participant characteristics

We will list general patient characteristics in a baseline characteristics table. Data will be presented as mean with standard deviation (SD) when normally distributed or as median with interquartile range in case of skewed data. Dichotomous and categorical data will be presented in proportions.

6. Analysis

6.1. Outcome definitions

6.1.1. Primary and secondary outcomes

Primary: Psychological well-being is the patient-centered effectiveness outcome (H1a) and remission from depression is the clinician-focused effectiveness outcome (H1b). Safety will be monitored through serious adverse events (H2a) as well as falls and fall-related injuries (H2b).

Secondary: Secondary tests of effectiveness will examine changes in other aspects of quality of life: physical function, social participation, changes in depressive symptoms (i.e., MADRS scores), and antidepressant response (i.e., 50% or more reduction from baseline MADRS).

Continuation phase analyses (all are considered secondary):

In the continuation phase, we will explore the long-term effectiveness and safety of antidepressants:

- We will examine long-term changes/stability of psychological well-being and other quality of life variables, and depressive symptoms, by mixed-effects repeated measures models.
- We will also test for sustained remission (among those who achieved remission at the end of the acute step) by measuring relapse in each arm. Relapse will be defined as meeting DSM 5 criteria for a major depressive episode, as determined by an Independent Evaluator − who will identify all remitted participants who then have a criterion-based (ie PHQ9 score of 2-3 for items 1-8, 1-3 for item 9) and who will confirm the diagnosis by conferring with a study investigator. We will carry out Cox models examining time to relapse (primary: meeting PHQ-9 criteria for a current MDE; secondary: MADRS ≥ 15).and time to drop out, to examine for treatment inferiority (i.e., whether one antidepressant strategy produces poorer long-term outcomes).
- In the continuation phase, we will also explore the long-term safety of antidepressants. **Serious adverse events** are the safety outcome in both acute and continuation phases. Cox models examining time-to-event (with Anderson & Gill extensions for repeated events) will compare the treatment arms during continuation in terms of serious adverse events. Since falls and fall-related injuries information were not collected during the acute phase, the safety endpoint has changed. A time-to-event analysis will not be appropriated. Hence, a generalized linear model with logistic link function will be used.

We will also compute rates of side effects in each arm, as specifically recommended by patient stakeholders. These data are not hypothesis-testing, but they support the patient-centered goal of allowing clinicians and patients to know what to expect in terms of side effects from treatment.

As well, the study will test how aging influences the relative benefits and risks of antidepressants for TRD. Additionally, a qualitative study of patient and clinician partners will provide the lived experience of TRD and antidepressant strategies.

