2.2.2. Hypothesis

Theme 1: Benefits and risks of antidepressants: outcomes that matter for patients and clinicians

- 1. Effectiveness. Augmentation arms will show greater improvement than monotherapy arms for effectiveness outcomes.
 - a. Wellness outcome: Improved psychological well-being. (H1a)
 - b. Symptom outcome: Remission from depression (defined as MADRS ≤10 at Step end).
 (H1b)
- 2. Safety. Augmentation arms will have more tolerability and safety concerns (i.e., more serious adverse events) than monotherapy arms.
 - a. Serious adverse events (H2a), falls, and fall-related injuries (H2b) are the safety outcomes.

The primary analytic strategy is a test of specific treatment strategies (e.g., aripiprazole augmentation). More recently, a report on these strategies in mixed-age veterans with TRD (Mohamed et al, JAMA 2017) has suggested that augmentation approaches yield higher remission rates than does switch. The TRD field has, likewise, converged on the overarching question of whether augmentation is superior to switch, more so than the specific question of which augmentation approach is superior (e.g., Ruberto, Jha, & Murrough, "Pharmacological treatments for patients with treatment-resistant depression", Pharmaceuticals 2020; Voineskos, Daskalakis & Blumberger, "Management of treatment-resistant depression", Neuropsychiatr Dis Treat 2020) with a recent Cochrane systematic review (Davies et al, 2019) determining that augmentation strategies appeared efficacious while switch strategies had uncertain efficacy.

For this reason, a secondary analysis of each hypothesis will test the overall strategy of augmentation vs. switch. The two augmentation arms in Step 1 will be summed and compared to the switch arm.

Theme 2: Aging influences the balance of benefits and risks of antidepressant strategies.

3. Moderator analyses (Heterogeneity of Treatment Effect). Exploratory analysis (HT-1): Effectiveness and safety differences between treatment arms will be moderated by age. Specifically, with increasing age effectiveness differences between treatment arms will decrease, and safety differences between treatment arms will increase. In addition, the following potential moderators will be assessed: executive function, co-morbid medical burden, co-morbid anxiety, and degree of treatment resistance.

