2.2.3. Scope

This Statistical Analysis Plan will be the guiding document for the quantitative analyses that will be conducted in the OPTIMUM study.

3. Study Methods

3.1. General Study Design and Plan:

Participants will be recruited from five regions with diverse and representative populations encompassing approximately 708 adults. The five regions are: St. Louis and rural Missouri; Los Angeles City and County; Pittsburgh and Western Pennsylvania; New York City; and Toronto and rural Ontario. Participants will be non-demented adults aged 60+, with equal proportions aged 60-70 and 70+, with current major depression that has failed to respond to 2+ adequate antidepressant trials. Two-thirds of the sample will be women and 86% White, 7% Black, 8% Latino/Hispanic, and 4% other racial groups.

All recruited adults will be randomized to 10 weeks of one of three Step 1 strategies: aripiprazole augmentation, bupropion augmentation, or switch to bupropion. Those who do not attain remission in Step 1 or those who do not qualify for Step 1 will be randomized to 10 weeks of one of two Step 2 strategies: lithium augmentation or switch to nortriptyline. Those who complete acute treatment will be followed in a one-year continuation, with assessments every four months. This pragmatic RCT will be carried out in real-world clinical settings. Primary care and mental health clinical partners will provide treatments, with decision support from the study team.

Patients will be identified from clinical networks at each of the five participating centers. Our two primary mechanisms of recruitment will be through screening and referrals. We will screen through clinical networks using Electronic Medical Records (EMR) and will contact all patients in practices aged 60 and older who in the recent past were prescribed or are currently taking antidepressants. Referrals will be elicited from practitioners and through advertisements to patients and their caregivers.

An additional mechanism of recruitment will be through IRB-approved hospital network registries and social media advertisements and posts on Facebook and Instagram. Potential participants who see Facebook ads and want to participate in the study can click on the Facebook ad and it will direct them to a secure and encrypted survey website using Redcap to collect name, phone number, and email address. Research study staff will contact the potential participants to screen them for study eligibility.

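### Relapse is compared between arms only among acute remitters, so the hazard ratio can be biased against a more effective strategy; it needs a sustained-remission comparison in all randomised beside it

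*SAP*

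**What the plan says.** SAP 6.1.1 opens its long-term section with "Continuation phase analyses (all are considered secondary". Three effectiveness analyses follow:

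- Mixed models of psychological well-being "and other quality of life variables, and depressive symptoms, by mixed-effects repeated measures models". No restriction to remitters is stated.
- A Cox model of time to relapse, as a test of sustained remission "among those who achieved remission at the end of the acute step". The primary relapse definition is based on PHQ-9 criteria for a current episode, the secondary on MADRS ≥ 15.
- A Cox model of time to drop-out.

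The two Cox models share one purpose: "to examine for treatment inferiority (i.e., whether one antidepressant strategy produces poorer long-term outcomes".

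Remission is one of the primary outcomes, H1b: "Remission from depression (defined as MADRS ≤10 at Step end" (SAP 2.2.2). SAP 4.3 adopts the intention-to-treat principle. On who is followed, SAP 3.1 says: "Those who complete acute treatment will be followed in a one-year continuation". Protocol H1 plans the same relapse test without stating the restriction to remitters, and calls these analyses exploratory. Neither document gives an adjustment for selection into remission, a caveat about it, or a comparison of sustained remission in everyone randomised.

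**The concern.** Remission at step end occurs after randomisation and is what the treatments are meant to change. SAP 2.2.2 expects augmentation to produce more remission than monotherapy. If it does, the augmentation remitters include patients who would not have remitted after a switch. Those extra remitters may be harder to keep well. The relapse HR would then count against the arm that helped more people, although no individual's relapse risk depends on treatment.

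The stated use makes this matter. Which strategy has the poorer long-term outcome is a question about everyone assigned to it. Relapse among remitters answers a narrower one: how durable remission is once reached. A reader given only the HR could take the answer to the second question as the answer to the first.

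**Working it through.** **The plan's own figures.** No sample size, HR or power is given for the relapse analysis. The nearest figure is the milestone of 900 participants finishing continuation (protocol K4), with 45% remission and 8% dropout per step and 10% continuation dropout.

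- Step 1 remitters: 0.45 × 1500 = 675; dropouts: 0.08 × 1500 = 120.
- Step 2 remitters: 0.45 × (1500 − 675 − 120) = 0.45 × 705 = 317.
- Total: 675 + 317 = 992; after 10% dropout, 0.90 × 992 = 893, close to 900.

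**Inputs from the documents.** Remission of about 40%, with 10 points called clinically meaningful (protocol H2). Revised total of 708, of whom 123 entered Step 2 directly (SAP 3.3), so 585 in Step 1. At 1:1:1 that is about 195 per arm.

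**Assumed.** Relapse rates; the documents give none. Everyone who remits on the lower-remission arm (A) would also remit on the higher one (B). Each patient's relapse risk is the same on either arm.

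**Mixture calculation.** A has 40% remission and B 50%, so 10 of B's 50 points are extra remitters. Let 12-month relapse be 30% in those who remit on either arm and x in the extra remitters.

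- Relapse among B's remitters = (0.40 × 0.30 + 0.10 × x) / 0.50.
- HR = ln(1 − relapse in B) / ln(1 − relapse in A).
- Sustained remission per randomised patient = remission × (1 − relapse).

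| x | Relapse, A | Relapse, B | HR, B vs A | Sustained, A | Sustained, B |
|---|---|---|---|---|---|
| 30% (equal) | 30% | 30% | 1.00 | 28% | 35% |
| 45% (1.5 times) | 30% | 33% | 1.12 | 28% | 33.5% |
| 60% (2 times) | 30% | 36% | 1.25 | 28% | 32% |

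For example, ln(0.64) / ln(0.70) = 0.446 / 0.357 = 1.25. With a base relapse of 20% in place of 30%, the last two HRs are 1.11 and 1.23.

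**Latent-vulnerability model.** Vulnerability is correlated with step-end severity and raises the relapse hazard by 0.7 to 1.0 on the log scale per SD. Relapse in arm A is 20% to 40%. At 50% against 40% remission:

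- correlation 0: HR 1.00;
- correlation 0.3: HR 1.03 to 1.05;
- correlation 0.5 to 0.7: HR 1.06 to 1.12.

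Remission rates below the documents' own enlarge the effect: 30% against 20% gives 1.08 to 1.18 at correlation 0.5 to 0.7. A differently parameterised latent model at 50% against 40% gave 1.08, 1.17 and 1.37 at correlations of 0.3, 0.5 and 0.7. The size therefore depends heavily on the assumptions.

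**Sampling error.** Log-rank simulation of the mixture, with 12 months of follow-up, 10% dropout and 4,000 runs per scenario. At 195 per arm there are about 78 and 98 remitters.

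| Relapse in extra remitters | HR > 1, 195 per arm | B significantly worse, 195 per arm | B significantly worse, 500 per arm |
|---|---|---|---|
| Equal | 51% | 2.3% | 2.5% |
| 1.5 times | 67% | 5.5% | 10.6% |
| 2 times | 79% | 11.0% | 27.0% |

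The nominal one-sided rate is 2.5%. At the revised size the distortion is mainly in the point estimate.

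**The case against.** The case for leaving the plan alone has five parts.

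1. **Relapse is not the only long-term test.** A reader might infer that it is. The documents do not support that: drop-out is tested for the same purpose ("and time to drop out, to examine for treatment inferiority"), and the mixed models carry no stated restriction to remitters. An arm with more remissions is also credited under H1b. This stands.
2. **The bias is conditional.** A reader might infer that the more effective arm's remitters will relapse more and that the ranking of arms will reverse. Nothing in the documents shows that extra remitters are more relapse-prone; if they are not, the bias is zero. This stands.
3. **A clean randomised long-term comparison is not simply waiting to be used.** Follow-up is of acute completers, itself a post-randomisation group. Step 1 non-remitters are randomised again, and relapsers may enter Step 2 (protocol F6). This stands against comparing continuation data from non-remitters. It does not block an outcome that counts non-remission and the move to Step 2 as not sustained.
4. **The composite can hide a real difference in durability.** Remission of 40% with 30% relapse and 50% with 44% relapse both give 28% sustained (0.40 × 0.70 and 0.50 × 0.56), although the relapse HR is ln(0.56) / ln(0.70) = 1.63. This stands. It is why the composite should be added beside the Cox model and should not replace it.
5. **The SAP names its population, and durability among remitters is a fair patient question.** True, but the stated purpose goes beyond durability, and no caveat limits the reading.

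**Conclusion.** The point holds in a limited form. The relapse comparison is made in a subset shaped by treatment, and its result is read as evidence on which strategy does worse in the long term. If extra remitters are more relapse-prone, the HR is biased against the more effective arm.

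At the documents' 40% remission and 10-point difference, the HR is 1.00 without selection, about 1.06 to 1.12 in the latent-vulnerability model at correlations of 0.5 to 0.7, and 1.12 to 1.25 if extra remitters relapse 1.5 to 2 times as often. These figures rest on assumed relapse rates and on no treatment effect on relapse. In the scenarios computed, sustained remission per randomised patient still favoured the arm with more remissions.

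The analyses are secondary in the SAP and exploratory in the protocol, so H1a and H1b are untouched. This is a worthwhile improvement, not a flaw in the trial's main conclusions.

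**What to change.** For each step, add a comparison of sustained remission in all participants randomised to that step.

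- **Definition.** MADRS ≤ 10 at step end and no MADRS ≥ 15 at months 4, 8 or 12. The MADRS threshold is the SAP's secondary relapse definition. It is the practical choice because MADRS is scheduled at those months, whereas PHQ-9 is not listed among the continuation assessments (protocol F2 and F6).
- **Not sustained.** Non-remitters and, for Step 1, anyone who moves to Step 2. SAP 6.3 already settles step-end status: early stoppers without a MADRS are non-remitters, and scores missing in completers are imputed.
- **Model.** The H1b logistic model, with three arms for Step 1 and two for Step 2.
- **Remitters lost during continuation.** Multiple imputation, with a sensitivity analysis counting them as not sustained.

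Keep the remitters-only Cox model. Label it a conditional, non-randomised comparison of durability, and state that it will not be used alone to conclude that a strategy has poorer long-term outcomes.

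The cost is one extra analysis per step on scheduled MADRS data and a sentence of labelling. The drawback is that the composite mixes remission with durability, so the two results must be reported and read together.
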